9.4 DEVICE FAILURES, MALFUNCTIONS AND NEAR INCIDENTS

Device failures or malfunctions will be reported to Sonex Health by the clinical sites. If the failure or malfunction results in an AE, the event shall be reported to the Sponsor within two (2) working days after the Investigator becomes aware of the event and reported to the IRB (if required) within the IRB required timeframe. The device involved in the incident should be returned to the Sponsor for evaluation.

9.5 REPORTING OF ADVERSE EVENTS

AEs will be recorded on the Adverse Event CRF and described by (a) duration (onset and resolution dates); (b) relationship to the study device or procedure; (c) action taken to resolve the event; (d) outcome of the event; and (e) whether or not such event is considered to have been serious. Additional information, such as procedural notes, treatment notes, or a signed clinical summary may be required as supporting documentation for the reported AE.

During the study, all deaths must be reported to the Sponsor within 48 hours and should also be reported on the End of Study CRF. A copy of the subject's death records, medical records for the events that led to the subject's death, and a death certificate (if available) should be provided.

Determination of whether a subject experienced an AE can be made in three different ways. First, an AE can be documented by the site during the study procedure. Second, a subject may report an AE directly via phone call to the investigative site. Third, an AE can be identified by the site during the review of the subject-uploaded wound healing images. If the site identifies a potential AE based on image review or is notified of a potential AE by the subject, confirmation of the AE will occur by a phone call with the subject or, if necessary, by asking the subject to return for a follow-up clinical evaluation.

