Mean BCTQ-SSS scores decreased by 1.2 (SE 0.07) points at 2 weeks, 1.3 (SE 0.07) points at 1 month, 1.6 (SE 0.09) points at 3 months, and 1.7 (SE 0.08) points at 1 year (p<0.001 at each follow-up interval). Mean BCTQ-FSS scores decreased by 0.6 (SE 0.06) points at 2 weeks, 0.9 (SE 0.07) points at 1 month, 1.1 (SE 0.07) points at 3 months, and 1.2 (SE 0.07) points at 1 year (p<0.001 at each follow-up interval). Mean QDASH scores decreased by 14 (SE 2) points at 2 weeks, 23 (SE 2) points at 1 month, 27 (SE 2) points at 3 months, and 32 (SE 2) points at 1 year (p<0.001 at each follow-up interval). No neurovascular injuries, tendon injuries, infections or significant post-surgical wound complications occurred, and there were no recurrences or reoperations reported in the study. One patient developed complex regional pain syndrome without evidence of nerve injury, which was promptly recognized and successfully treated. This patient ultimately had CTR-US performed on the contralateral hand.

The purpose of this prospective multicenter study is to determine the safety and effectiveness of CTR-US when performed in an office setting.

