7.2.2 Follow-up Assessments

A list of the study assessments performed by the investigational site at each study interval is provided in the table below.

Assessment	Baseline Screening	Procedure	Post- Op	Day 7	Day 14	1 month	3 months	6 months	12 months	24 months
Demographics	\checkmark									
Ultrasound median nerve cross-sectional measurement ¹	4									
CTS-6 ²	√									
Procedure		\checkmark								
Adverse events		\checkmark	\checkmark	V	\checkmark	\checkmark	\checkmark	\checkmark	V	\checkmark

¹Required for all treated hands.

²Measured on both hands

A list of the patient reported outcomes provided by the patient at each study interval is provided in the table below.

Assessment	Baseline Screening	Procedure	Post-Op	Daily 1-14	1 month	3 months	6 months	12 months	24 months
Demographics	1								
Medical history	\checkmark								
BCTQ-SSS ¹	√			√ ²	\checkmark	\checkmark	1	1	\checkmark
BCTQ-FSS	√			√ ²	1	1	1	1	1
MHQ	√			√ ²	1	1	1	1	1
EQ-5D-5L	1			√ ²	1	√	1	1	1
Numeric Pain Scale ¹	√	√	V	√	V	√	√	√	√
Procedure		$\sqrt{1}$							
Return To Activities				√	V	√	1	1	1
Return To Work ³				\checkmark	\checkmark	√			√
Pain Medication	√	√	V	\checkmark	\checkmark	√	√	√	\checkmark

¹Measured on all treated hands.

²Collected only at 14-day evaluation

³Employed subjects only

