7.2.3 Unscheduled Follow-up Visits

If subjects are seen for unscheduled visits because of an AE or additional hand surgery, appropriate Case Report Form(s)will be completed, if applicable.

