9. ADVERSE EVENTS

An Adverse Event (AE) is defined as any adverse change (i.e., de novo or preexisting condition) from the subject's baseline medical condition occurring after the initial procedural incision has been initiated. Any AE which resolved and then recurred will be reported as a separate AE. A pre-specified listing of AEs will be documented on the Adverse Event eCRF.

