11.9.3 Protocol Deviations

A protocol deviation is an unplanned excursion from the protocol that is not implemented or intended as a systematic change. An Investigator who fails to perform tests or examinations as required by the protocol or failures on the part of study subjects to complete scheduled visits as required by the protocol, would be considered protocol deviations. These types of deviations are reported to the Sponsor and in accordance with the IRB policy.

A Protocol Deviation CRF must be completed by the site for each study protocol deviation (e.g., failure to obtain informed consent, enrolling a subject who does not meet inclusion / exclusion criteria, not performing required testing, missed follow-up window, etc.). An Investigator must notify the Sponsor and the reviewing IRB of any deviation from the study protocol that was done to protect the life or physical well-being of a subject. Such notice should be given as soon as possible, but no later than five (5) working days after the emergency occurred.

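### Sites must assess adverse events at every interval to 24 months, but the only post-procedure routes described wait for the subject to act, so related events might be under-counted

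*Combined protocol and SAP*

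**What the plan says.** Section 7.2.2 opens its first table with "A list of the study assessments performed by the investigational site at each study interval is provided in the table below". The AE row is ticked at the procedure, post-op, days 7 and 14, and 1, 3, 6, 12 and 24 months. Section 11.9.3 counts as a deviation "An Investigator who fails to perform tests or examinations as required by the protocol", so the AE assessment can be read as required. The second table in 7.2.2 covers patient-reported items. It has no AE question and no wound-image upload. The synopsis describes post-procedure contacts as remote, subject-reported eVisits.

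Section 9.5 describes how AEs are found: "Determination of whether a subject experienced an AE can be made in three different ways". The first way is documentation by the site during the procedure. The others are: "Second, a subject may report an AE directly via phone call to the investigative site" and "Third, an AE can be identified by the site during the review of the subject-uploaded wound healing images". A call with the subject, or if needed a clinic visit, then confirms a potential AE that has already surfaced.

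The AE outcomes are in 8.2.7 (definitely or probably related events within 90 days, a secondary endpoint) and 8.2.9 (related and serious related events at intervals to 24 months). Section 10.2.3 plans per-subject incidence with Clopper-Pearson 95% intervals.

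**The concern.** The schedule requires an AE assessment from the site, and the text does not say how the site carries it out. Once the procedure is over, both routes named in 9.5 start with the subject.

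A wound image is a reasonable screen for visible wound problems. It is a poor one for events without a visible sign. Section 5 gives two examples from earlier studies: "One patient developed complex regional pain syndrome without evidence of nerve injury", and one incomplete release confirmed at reoperation. Neither kind of event need show on an image.

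Safety is part of the trial's stated objective, and there is a single arm, so missed events cannot balance out between groups. They lower the reported incidence directly. Sites may also complete the same AE row in different ways, which would make rates hard to compare across up to 12 sites.

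**Working it through.** The documents state no expected AE rate, detection rate or precision target for AEs, so there is no plan figure to reproduce. The check is a reading of the passages, followed by an illustration.

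**1. Does any other passage supply a solicited query?**

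| Section | What it provides | Closes the gap? |
|---|---|---|
| 7.2.2, patient-reported table | Pain, symptom, function, quality-of-life and medication items | No AE item, and no rule that a worse answer prompts AE review |
| 7.2.3 | CRFs completed as applicable: "If subjects are seen for unscheduled visits because of an AE or additional hand surgery" | No, the subject is already being seen |
| 7.2.4 | At least two contact attempts | No, only for subjects who miss follow-up |
| 7.3.2 | Withdrawal after certain later hand surgery | No, it assumes the site learns of the surgery and gives no method |
| 9 | "A pre-specified listing of AEs will be documented on the Adverse Event eCRF" | Not by itself: it governs what is recorded, not whether subjects are asked |
| 9.6 and 9.7 | Adjudication of AEs, and review of AE incidence | No, neither is given a role in finding unreported events |
| 11.7 | Site records of AE observations and subject condition | No, record keeping only |

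**2. Direction of the bias.** Let p be the true share of subjects with a related AE and s the share of those subjects detected. The expected reported rate is p × s, which is below p whenever s < 1. The Clopper-Pearson interval describes sampling error around p × s and contains no term for s.

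**3. Illustration, with p and s assumed.** n = 140 is the enrolment minimum in 10.1. The reported count is X ~ Binomial(140, p × s). The lower columns sum P(X = k) over every k whose exact 95% upper limit is below p. At n = 140 the upper limits are 2.6% for 0 events, 3.9% for 1 and 5.1% for 2.

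| Assumed true rate p | Expected reported rate at s = 50% | Upper limit below p: s = 100% | s = 75% | s = 50% |
|---|---|---|---|---|
| 1% | 0.5% | 0% | 0% | 0% |
| 2% | 1.0% | 0% | 0% | 0% |
| 3% | 1.5% | 1.4% | 4.1% | 12.1% |
| 5% | 2.5% | 0.6% | 3.1% | 13.3% |
| 10% | 5.0% | 1.1% | 9.3% | 44.6% |

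For example, at p = 5% and s = 50% the expected count is 140 × 0.05 × 0.50 = 3.5 subjects instead of 7.0.

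Below a true rate of 2.6% the upper limit cannot fall under the truth, because even 0/140 gives 2.6%. There the harm is to the estimate. The chance of reporting no events is (1 − p × s)^140:

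- p = 1%: 0.99^140 = 24.5% with full detection, and 0.995^140 = 49.6% with half detected.
- p = 2%: 0.98^140 = 5.9% with full detection, and 0.99^140 = 24.5% with half detected.

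**4. Can the documents narrow these ranges?** Hardly. Section 5 gives 1/346 for incomplete release (0.3%, exact 95% CI 0.01% to 1.6%). It gives one complex regional pain syndrome, which is 1/88 (1.1%, exact 95% CI 0.03% to 6.2%) if that patient is among the 88 with 1-year data, an assumption. Both are single event types and narrower than all related AEs. Nothing in the documents bears on s.

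**The case against.** The strongest reply is that silence about method is not evidence of passive surveillance. An AE assessment assigned to the site ordinarily means that the site checks. The site table is separate from the patient-reported one and has its own day 7 and day 14 columns, so a remote eVisit for questionnaires does not prove that no site contact lies behind the AE row. Section 9.5 says determination can be made in these ways, which is not exclusive. The withdrawal rules and the record-keeping duties presuppose that sites learn of reoperations and of each subject's condition, which weakens the incomplete-release example. The AE eCRF and the Monitoring Plan are not among the documents and may contain a prompt.

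Most of this stands as a limit on the conclusion. A reader might infer that an event neither phoned in nor visible on an image would be lost. The documents do not support that, for the reasons just given; they support only that it might be.

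It does not remove the point. Section 9.5 sets out an enumerated method for finding AEs, its post-procedure routes are both subject-initiated, and no other section adds a routine query. If the ticks do mean that sites ask, the text should say so, because sites answer for required assessments.

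It is also fair that trial success depends only on the BCTQ-SSS and that the AE endpoint is secondary and descriptive. Safety is nevertheless a stated objective.

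**Conclusion.** The point holds as a risk of under-counting. Sections 7.2.2 and 9.5 do not fit together: AE assessments are scheduled to 24 months, and the described post-procedure routes depend on the subject acting first. Related events that do not show on a wound image might be missed in the 90-day endpoint and in the later AE outcomes.

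Any bias would be downward, and the exact intervals would not reflect it. Its size is unknown. A reader might take the illustrative percentages as an estimate for this trial, but both the true rates and the detection shares are assumed. The 44.6%, for instance, needs a 10% true rate together with half of affected subjects missed.

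Confidence is medium, since the unseen AE eCRF could already contain the query. The change should be made, because it is cheap and events not asked about at the time may not be fully recoverable later.

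**What to change.** - Add one solicited, non-leading ePRO question at the existing day 7, day 14 and 1, 3, 6, 12 and 24-month contacts. It should ask about any new or worse health problem since the last contact, any medical care sought, and any further hand surgery. It should not be confined to the treated hand or wrist: section 9 defines an AE as an adverse change from the baseline medical condition, and 9.3 counts anesthesia complications as procedure-related.
- Let a 'yes' trigger the confirmation call that 9.5 already describes.
- State in 9.5 and 7.2.2 that the site AE row is completed from this query plus the existing routes, including unscheduled visits, and show the query and the wound-image upload in the schedule.
- Report the number of subjects who answered the query beside the per-subject AE incidence, since an ePRO item also depends on response.
- If the AE eCRF already directs such a query, say so in 9.5.

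The cost is one more question per contact, some extra confirmation calls, and probably a somewhat higher reported AE rate. No visit or test is added.

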9.6 INDEPENDENT MEDICAL REVIEWER

Evaluation and adjudication of all AEs will be performed on an ongoing basis by an independent medical reviewer. The independent medical reviewer will review AEs for AE classification, seriousness, and relationship to the device or procedure. Discrepancies between the investigational site and the independent medical reviewer will be handled by discussion, with the determination by independent medical reviewer serving as the final classification.

9.7 DATA SAFETY MONITORING BOARD

A Data Safety Monitoring Board (DSMB) will oversee enrollment and safety of the subjects for the study. Members of DSMB will be independent of the sponsor and investigational sites. The DSMB for the study will consist of three (3) clinicians with expertise in orthopedic or plastic surgery, and with experience and expertise in clinical trials. The DSMB will convene at least once during the subject enrollment period and will review, at a minimum, subject enrollment status and incidence of AEs. Based on a review of these data, the DSMB will advise the Sponsor to continue the trial with no modification, or to modify the trial as appropriate if enrollment or safety concerns are identified.

9.8 RISK-BENEFIT ANALYSIS

9.8.1 Risk Analysis

Complications and risks that exist for other CTR treatments may also exist for carpal tunnel release using UltraGuideCTR and real-time ultrasound guidance. UltraGuideCTR has undergone extensive risk analysis testing and is designed with safeguards built into the device to mitigate the serious risks. The full list of anticipated adverse events is provided on the Adverse Event CRF.

9.8.2 Potential Benefits

The data obtained from this study will be used to document the safety and effectiveness of UltraGuideCTR when performed in an office-based setting. The data derived from this study may benefit individuals with CTS in the context of a shared decision-making process when contemplating CTR. In addition, subjects potentially could directly benefit from participation in this study. Treatment with UltraGuideCTR and real-time ultrasound guidance in an in-office setting may potentially allow for rapid return to work and normal daily activities, as well as avoidance of general anesthesia and the costs associated with treatment in a hospital or ambulatory surgery center.

10.DATA ANALYSIS

This is a prospective, multicenter, single-arm trial designed to evaluate the safety and effectiveness of office-based CTR-US in treating subjects with symptomatic CTS.

10.1 SAMPLE SIZE JUSTIFICATION

This study will enroll a minimum of 140 subjects who will receive office-based CTR-US. This sample size provides adequate statistical power for the evaluation of the primary endpoint given the assumptions below:

- Primary endpoint: BCTQ-SSS change at 3 months
- Statistical test: Linear mixed model
- Two-tailed alpha: 0.05
- Standard deviation change in BCTQ-SSS at 3 months: 0.75 points
- Subject attrition: 15%

The results of this power analysis show that a sample size of 100 evaluable subjects provides 90% statistical power to detect a mean change of 0.2 points on the BCTQ-SSS at 3 months. To account for reasonable subject attrition, a minimum of 140 subjects will be enrolled in the trial.

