Patients completed a preoperative questionnaire, daily post-operative text message questions for up to 14 days post procedure, and emailed questionnaires at 2 weeks, 1 month, 3 months, and 6 months postoperatively. Pre-treatment patient assessments included demographic data, medical and surgical history, work status, and patient-reported outcomes including the Quick form of the Disabilities of the Arm, Shoulder, and Hand Questionnaire (QDASH) and Boston Carpal Tunnel Symptom Severity and Functional Status Scores (BCTQ-SSS and BCTQ-FSS). Return to normal activities and return to work were collected via daily text messages for the first 14 days. Thereafter, postoperative outcomes were collected via e-mail or text message and included QDASH, BCTQ-SSS, BCTQ-FSS, return to normal activities, return to work, and patient satisfaction.

Co-primary endpoints of this study were QDASH, BCTQ-SSS, and BCTQ-FSS. The QDASH is an 11-item patient-reported questionnaire that has been validated for CTS, where the total score ranges from 0 (indicating no disability) to 100 (indicating most severe disability) ³⁴. The BCTQ is a CTS specific questionnaire consisting of 11 symptom severity questions (BCTQ-SSS) and 8 functional status questions (BCTQ-FSS). Scoring for the BCTQ- SSS and BCTQ-FSS ranges from 1 to 5, with higher scores indicating more severe symptoms and more severe disability, respectively ³⁵. Minimal clinically important differences (MCIDs) for the postoperative change in patient-reported outcomes were 15 points for QDASH ³⁶, 1.14 points for BCTQ-SSS ³⁷, and 0.74 points for BCTQ-FSS ³⁷. Return to normal activities was ascertained by asking patients when they had returned to normal daily activities outside of work. Return to work was ascertained by asking employed patients when they had returned to work in any capacity, a definition that is commonly used among CTS studies ^{38,39}. Patient satisfaction with the procedure was reported on a 5-point Likert scale ranging from 1 (very dissatisfied) to 5 (very satisfied); a score of 4 or 5 indicated that a patient was satisfied with the procedure. Postoperative complications were recorded via chart review performed by the treating physician.

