Among 535 patients who enrolled in the registry and provided postoperative follow-up, data were available on 499 (93%) patients at 2 weeks, 475 (89%) at 1 month, 446 (83%) at 3 months, and 373 (70%) at 6 months. The cohort of 373 patients with 6-month follow-up formed the basis for the report. Between November 2019 and July 2021, 373 patients (427 hands, mean age 55 years, 71% female, 62% employed) underwent CTR-US at 24 sites in the United States. A total of 329 (88.2%) procedures were performed using local anesthesia, 44 (11.8%) were performed using monitored anesthesia care, and no procedures were performed using general anesthesia. There were 217 unilateral CTR-US procedures, 51 staged bilateral CTR-US procedures, and 54 simultaneous bilateral CTR-US procedures. Simultaneous procedures consisted of 14.5% of cases and 25.3% of treated hands.

Patient-reported measures of symptom severity and physical function demonstrated rapid improvement following CTR-US. Mean QDASH scores were 41.7 ± 20.1 at baseline, 21.4 ± 15.9 at 2 weeks, 17.7 ± 15.1 at 1 month, 13.3 ± 15.0 at 3 months, and 11.0 ± 15.2 at 6 months. QDASH scores decreased by 20.3 (95% CI: 17.5 to 23.0) points at 2 weeks and 30.8 (95% CI: 28.1 to 33.4) points at 6 months (p<0.001 at each follow-up interval). Mean BCTQ-SSS scores were 3.0 ± 0.7 at baseline, 1.7 ± 0.6 at 2 weeks, 1.7 ± 0.6 at 1 month, 1.5 ± 0.6 at 3 months, and 1.4 ± 0.6 at 6 months. BCTQ-SSS scores decreased by 1.3 (95% CI: 1.2-1.4) points at 2 weeks and 1.6 (95% CI: 1.5-1.7) points at 6 months (p<0.001 at each follow-up interval). Mean BCTQ-FSS scores were 2.4 ± 0.8 at baseline, 1.7 ± 0.6 at 2 weeks, 1.6 ± 0.5 at 1 month, 1.4 ± 0.5 at 3 months, and 1.3 ± 0.5 at 6 months. BCTQ-FSS scores decreased by 0.7 (95% CI: 0.5-0.8) points and 1.0 (95% CI: 0.9-1.1) points at 2 weeks and 6 months, respectively (p<0.001 at each follow-up interval).

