The median time to return to normal activities following CTR-US was 3 days (interquartile range [IQR]: 2-5 days), with 96.5% of patients reporting returning to normal activities within 2 weeks of the procedure. Among employed patients, the median time to return to work following CTR-US was 5 days (IQR: 3-9 days), with 92.3% of patients reporting returning to work within 2 weeks of the procedure. The median time to return to work based on employment type was 4 days (IQR: 3-6 days) for desk-based occupations, 6 days (IQR: 4-11 days) for light manual occupations, and 5 days (IQR: 3-14 days) for heavy manual occupations. The percentage of patients who were satisfied or very satisfied with the procedure was 91.6% at 2 weeks, 88.2% at 1 month, 88.0% at 3 months, and 89.8% at 6 months.

Among 346 (93%) patients with available complication data, no major neurovascular complications were reported. Specifically, there was 1 (0.3%) incomplete release confirmed

during reoperation and no reports of superficial infection, deep infection, arterial laceration, or permanent nerve injury.

A recent study by Bergum and Ciota ³³ demonstrated the feasibility of CTR-US when performed in an office-based setting. This was a prospective single-center study that evaluated 1-year outcomes in patients treated with office-based CTR-US. Among 88 patients (123 hands) with 1year follow-up data, 29 patients (57 hands) were treated with simultaneous bilateral procedures, 18 patients (25 hands) were treated with staged bilateral procedures, and 41 were treated with a unilateral procedure. All office-based procedures were successfully completed with local anesthesia and no intraoperative complications occurred.

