10.2.3 Data Analysis Methods

Baseline data will be analyzed using descriptive statistics. Continuous data will be summarized using mean and standard deviation for normally distributed data, median and interquartile range for non-normally distributed data, and counts and percentages for categorical data. For categorical variables, percentages will be calculated based on non-missing data.

The primary endpoint will be reported as the mean change in BCTQ-SSS at 3 months relative to baseline. Data will be reported as the mean change and 95% confidence interval. A linear mixed model will be the statistical test used to assess the primary endpoint, which accounts for the correlation inherent with bilateral procedures ⁴¹. The study will be deemed successful if the mean BCTQ-SSS score at 3 months is statistically significantly lower than at baseline, as determined by a p-value less than 0.05 using the linear mixed model.

Time to return to normal daily activities and time to return to work among employed individuals will be reported as the median and interquartile range in each treatment group.

Longitudinally measured continuous outcomes (i.e., BCTQ-SSS, BCTQ-FSS, MHQ, Numeric Pain Scale, EQ-5D-5L) will be analyzed using a linear mixed model.

Adverse events will be reported using counts, percentages and exact 95% confidence intervals using Clopper-Pearson's method. Calculation of AE incidence will be performed on a persubject basis.

Statistical analyses will be performed using a two-sided hypothesis test at a 5% level of significance. No adjustments for multiplicity are planned. Missing data imputation will not be performed. Subgroup analyses will be performed for subjects undergoing a unilateral or bilateral simultaneous procedure.

11.STUDY RESPONSIBILITIES AND MANAGEMENT

This study will be performed in accordance with all requirements set forth in the U.S. regulations, 21 Code of Federal Regulations (CFR) Parts 812, 50, 54, and 56, the Declaration of Helsinki, and any other applicable local laws, regulations, or guidelines.

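### The 90% power in Section 10.1 does not follow from its listed assumptions: with one hand per subject, 100 evaluable subjects give about 75% power for a 0.2-point change

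*Combined protocol and SAP*

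**What the plan says.** Section 10.1 says that a minimum of 140 subjects gives adequate power for the primary endpoint, the change in BCTQ-SSS at 3 months, under a short list of assumptions. The test is a linear mixed model and alpha is 0.05, two-tailed. The variability is given as "Standard deviation change in BCTQ-SSS at 3 months: 0.75 points", and the dropout line reads "Subject attrition: 15" per cent. The result is that "100 evaluable subjects provides 90% statistical power to detect a mean change of 0.2 points on the BCTQ-SSS at 3 months", with 140 enrolled to allow for attrition.

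Section 10.2.3 sets the success rule: "The study will be deemed successful if the mean BCTQ-SSS score at 3 months is statistically significantly lower than at baseline". It adds that the mixed model handles the correlation between the two hands of bilateral subjects. Section 10.1 gives no bilateral share, no between-hand correlation and no correlation between visits.

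**The concern.** For a single-arm trial that compares a 3-month mean with baseline, the standard deviation of change, sample size, alpha and effect size together fix the power. A quick check with the listed values falls well short of 90%. The attrition step does not connect either: 15% attrition from 140 leaves 119, not 100.

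Section 10.1 is the plan's only quantitative justification of the sample size. A statistician, ethics board or journal that checks it will not be able to reproduce it. What is at stake is the accuracy of the stated power, not the chance that the primary test succeeds.

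**Working it through.** **Inputs.** From Section 10.1: SD of change 0.75, two-sided alpha 0.05, 100 evaluable subjects, effect 0.2, stated power 90%, attrition 15%, 140 enrolled. The base case assumes one hand per subject and both visits observed, so the mixed model reduces to a one-sample test on the change score.

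**1. The plan's own figure.** The noncentrality is 0.2 / (0.75/√100) = 0.2/0.075 = 2.667.
- Normal approximation: Φ(2.667 − 1.960) = 76.0%.
- Noncentral t, 99 df: 75.2%.

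The stated 90% is not reproduced. A one-sided test at 0.05 would give 84.2%, and the plan specifies two-tailed.

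**2. Power for 0.2 points at other sample sizes (noncentral t).**

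| Evaluable | Basis | Power |
|---|---|---|
| 100 | as stated | 75.2% |
| 119 | 140 × 0.85 | 82.3% |
| 140 | no attrition | 88.0% |
| 150 | smallest n reaching 90% | 90.1% |

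By the normal approximation, the n for 90% is [0.75 × (1.960 + 1.282)/0.2]² = 147.8, so 148.

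**3. What would make 90% true at n = 100.** Either an effect of 0.2455 points (normal approximation: 0.75 × 3.242/10 = 0.243), or an SD of about 0.61. At 119 subjects, 90% power corresponds to 0.2247 points.

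**4. Attrition.** 100/0.85 = 117.6, so 118 enrolled would be enough for 100 evaluable. Going from 140 to 100 implies 1 − 100/140 = 28.6% attrition, not 15%. The margin is unexplained but in the safe direction.

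**5. Could the mixed model recover the gap?** Section 10.1 gives no inputs for this, so the following are assumptions taken from Section 5.

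- *Unpaired baselines.* Suppose there are 140 baselines and 100 three-month scores. Registry SDs are 0.7 (baseline) and 0.6 (3 months). An SD of change of 0.75 then implies a correlation of (0.49 + 0.36 − 0.5625)/(2 × 0.7 × 0.6) = 0.342. The generalised least squares variance of the mean change is 0.00493, equivalent to 0.5625/0.00493 ≈ 114 complete pairs. Power is about 81%.
- *Bilateral hands.* With bilateral share f and between-hand correlation ρ, the effective n is n × [(1 − f) + 2f/(1 + ρ)]. The registry says "Simultaneous procedures consisted of 14.5% of cases". In the office-based study "29 patients (57 hands) were treated with simultaneous bilateral procedures", out of 88 patients, so f is about 0.33.

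| Subjects | Lowest (f = 0.145, ρ = 0.9) | Highest (f = 0.33, ρ = 0) |
|---|---|---|
| 100 | effective n 100.8, power 75.5% | effective n 133.0, power 86.3% |
| 119 | effective n 119.9, power 82.5% | effective n 158.3, power 91.5% |

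- *Both together, 100 subjects with 3-month data.* With f = 0.33, power is 90.4% at ρ = 0, 89.1% at ρ = 0.1 and 84.6% at ρ = 0.5.

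**6. Power for the changes expected.** Section 5 gives an MCID of "1.14 points for BCTQ-SSS" and, for the office-based study, a fall of "1.6 (SE 0.09) points at 3 months". At n = 100, power for 0.5 points already exceeds 99.99%. For 1.14 points (noncentrality 15.2) and 1.6 points (21.3) it is effectively 100%.

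**The case against.** Three objections deserve weight.

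**Rounding.** At 100 subjects, 90% power corresponds to 0.2455 points, which prints as 0.2 at one decimal place. This is a plausible and harmless explanation. It stands as an inference, but the documents do not confirm it. The printed figure matters as printed: 0.2 points needs 150 evaluable subjects, not 100.

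**The test is a mixed model on all treated hands.** The 75% holds for one hand per subject with complete pairs; bilateral hands and unpaired baselines both add information. This stands in part. Taken singly at 100 subjects, and with the previous studies' bilateral shares, neither source reaches 90%. Taken together they just reach it, at a one-third bilateral share and zero correlation between a subject's two hands, which is an unlikely corner. Larger bilateral shares could also reach it: about half of subjects bilateral at zero correlation, for example, gives an effective n of 150. None of these inputs is listed in Section 10.1, so they cannot support a statement said to rest on the listed assumptions.

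**No practical consequence.** This stands. No analysis or conclusion depends on the 0.2-point figure, and power for any change near the MCID is essentially complete. It limits the importance of the point but does not make the sentence correct.

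**Conclusion.** The concern holds. On the listed inputs, with one hand per subject and both visits observed, the stated power is about 15 percentage points too high. Equivalently, the stated detectable change is about 0.045 points too small. Enrolling 140 does not restore the claim, either at 15% attrition or with none. The documents do not show which of the five figures is wrong.

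This is a definite error in a key statement with little consequence for the trial. It should be corrected, but it gives no reason to enlarge the study or change its success rule. Confidence in the base-case arithmetic is high. The only uncertainty is whether undisclosed bilateral or mixed-model inputs lay behind the original calculation.

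**What to change.** Reword Section 10.1 in one of three ways.

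- **Use the expected evaluable number.** For example: 140 enrolled with 15% attrition leaves 119 evaluable subjects, giving about 82% power for a mean change of 0.2 points and 90% power for about 0.225 points (SD of change 0.75, two-sided alpha 0.05, one hand per subject).
- **Keep 100 as a planning floor.** State 90% power for 0.25 points (computed 91.0%), and explain that 140 allows for up to about 29% attrition rather than 15%.
- **Disclose further inputs.** If the original calculation counted both hands of bilateral subjects, or used unpaired baselines, state the bilateral share and the correlations assumed, and show the resulting power.

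The cost is a wording change in this section. The stated power for 0.2 points, or the stated detectable change, becomes slightly less favourable.
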